7. **Salivary cotinine** (measured at Intake and at the half-way point): Participants will be directed to use a saliva collection aid with a cryovial for collection of 1ml saliva sample. Saliva sample can only be collected at least one half hour after eating or drinking. Saliva samples will be frozen at -20°C. Cotinine will be measured with an EIA (Enzyme-immunoassay) (148). (See salivary cotinine test procedures in appendix 4 for details). Saliva samples will be transported to MSK BAIC Core facilities for temporary storage, until shipped to Drs. [name] and [name] at NYU for analysis.
8. **Epigenetic changes** (at Intake): We will use the minimally invasive buccal cell approach to identify traffic pollution-related epigenetic biomarkers in taxi drivers, because gene expression changes induced by inhaled pollutants in human subjects in buccal and/or nasal cells reflect those in bronchial epithelium (76, 149, 150). Buccal cells will be collected from study participants by gently scraping both left and right inner cheeks using special collection brushes (Gentra Puregene Buccal Cell Kit, Qiagen, Valencia CA). Methylation-specific PCR (MSP) (151) will be performed as routinely (134), using HotStar Taq DNA Polymerase kit (Qiagen), using MSP primers identified from the literature. Methylated (M) or unmethylated (U) status will be denoted per gene per participant. Buccal samples will be transported to MSK BAIC Core facilities for temporary storage and later shipped to collaborators at NYU for analysis. (See buccal swab test procedures in appendix 4 for details)

PAH (Polycyclic Aromatic Hydrocarbon) will be assessed via urine sample collection of Urinary 1 hydroxy pyrene and particulate matter collected via Polyurethane Foam Filter (PUF) sampler:

9. **PAH via Urinary 1 hydroxy pyrene**: Drivers will be asked to give a urinary sample twice during the study. The first urine sample will be collected on the morning at the end of the first or second work week of study. The second sample will be collected from drivers on the morning of the end of the fourth week of study participation. Drivers will be provided with a 100 cc sterilized

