Pyrosequencing to detect global genome methylation levels (approximated by LINE-1 repeat methylation) will be performed per Colella (153) using a PSQ96MA System (Biotage/Qiagen). Recent studies show decreased LINE-1 methylation following exposure to traffic particulates, PM_{2.5} and carbon black (71). Because pyrosequencing quantifies percent methylation of individual CpG sites, we can also use it for quantitative analysis of percent methylation of genes in the reference panel above, to supplement the qualitative M/U calls made by MSP. While the gene choices in a candidate gene approach are vast, support for the particular genes chosen here is evident in a recent study of non-small cell lung cancer in Asians (China) showing good correlation for **RASSF1A**, **RARB**, **hMLH1**, **p16**, **RUNX3** and **DAPK** with lung cancer (154).

Due to the nature of the study, staff will handle and transport biological specimens that are categorized as potential toxic and infectious substances (dangerous goods-class 6, category b) To ensure good clinical practice procedures are followed, before study activation, all staff will complete the Dangerous Goods Shipping training and complete any additional MSKCC courses on handling biologic materials. Additional biospecimen collection training procedures will be provided by New York University.

A reminder system will be set up to increase study adherence. To remind participants to carry dataRAMs to work we will have daily text messages sent to mobile phones. We will provide participants with a friendly door knob sign to take home and place on bedroom doors as an additional reminder to carry their portable dataRAM monitors to bed and as a visual cue to remind them to make sure to take it with them when they leave for work.

Feasibility Data

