11.0 BIOSTATISTICS

Overview. This pilot study follows a two parallel arm design. Drivers will be randomized to one of two groups, an Intervention Group (an in-vehicle HEPA filter will be provided) and a Wait-list Control Group (HEPA filter will be provided at the end of wait-list period). We plan to recruit a sample of n=14 participants in each group (n=11 per arm with analyzable (non-missing) data, assuming a 25% drop-out rate as described below).

General analytic strategies. The general data analytic paradigm for this pilot study will be descriptive statistics only. The aim is to collect pilot data to help guide a future randomized intervention study. Descriptive statistics and assessments of correlations will be sought to address the aims (see below). The sample size of 14 per condition was primarily determined by resources limitations. A sample of 14 per condition was deemed possible within the funding resources of no more than 2 years.

Analytic plans for the Specific Aims.

Aim 1a: The primary aim will be to collect preliminary data on in-vehicle excess PM exposure.

Descriptive statistics (means and standard deviations) will be sought on: 1) PM size distribution 2) mass concentration, and 3) chemical composition for all three groups. These observations will be used to evaluate to what extent the two groups were exposed to these environmental hazards. For each study participant, an area-under-the-curve (AUC) summary will be sought for each of the three PM measurements over appropriate time periods. Generally, a daily average will be calculated from the hourly PM assessments. Then the AUC of the 28 daily averages will be calculated per person to represent the summary of PM exposures during study participation.

Aim 1b: To conduct a preliminary assessment of the correlation between PM exposure and physiologic and biochemical markers associated with increased risk of lung cancer and/or CVD.

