For each group, a correlation matrix will be constructed between the three components of the AUC outcomes described in Aim 1a and a set of physiologic and biochemical markers. Generally, Pearson's correlation coefficients will be sought. If preliminary analyses found the variables to be skewed, then Spearman's rank correlation coefficients will be calculated instead. The purpose of these correlation coefficients are to examine the associations between the environmental exposure to air pollutants and physiologic and biochemical markers. Point-biserial correlation coefficients will be sought between the continuous AUC summaries of PM data and other binary variables of interest (e.g., methylation). These correlation coefficients can be sorted in descending order to help identify the top candidates of physiologic and biochemical markers that are most likely to be associated with PM exposure. Care will be taken to match the variables by time, using the time stamps from the PM measurements and the date of biomarker serum collection. For example, the AUC of PM in the first week will be associated with serum cytokines measured during the first week. This work will have to be done in a post-hoc manner, after we have all data sources. Then we will evaluate the best strategies to link them together by time. It helps to have automatic time stamps by the PM measurement devices, which is likely to minimize coding errors and missing data.

Aim 2: To use a randomized wait-list controlled design to conduct a pilot study of whether a targeted intervention, installation of a portable car high-efficiency particulate air (HEPA) filter (to remove PM), results in a reduction of in-vehicle PM exposure and associated physiologic and biochemical markers among taxi drivers..

We will calculate the difference in the three PM components and in physiologic/biochemical markers between the HEPA intervention condition and the Wait-List Control condition to obtain the pilot data needed for a future, larger study with the potential to provide remediation to potential harmful exposures to air pollution among NYC taxi drivers.

Aim 3: To collect feasibility data on conducting the proposed randomized wait-list controlled pilot study among New York City taxi drivers.

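### Aim 1b allows methylated/unmethylated calls to be ranked in one list with continuous markers, where a gene tends to fall below an equally associated continuous marker, and the analysis section never uses percent methylation.

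*Combined protocol and SAP*

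**What the plan says.** Under Aim 1b, Section 11.0 describes the matrix as follows: "For each group, a correlation matrix will be constructed". Its rows and columns are the PM AUC summaries and the physiologic and biochemical markers. The default coefficient is Pearson's ("Generally, Pearson's correlation coefficients will be sought"), with a fallback: "If preliminary analyses found the variables to be skewed, then Spearman's rank correlation coefficients will be calculated instead". Binary variables are treated differently, and methylation is the named example: "Point-biserial correlation coefficients will be sought between the continuous AUC summaries of PM data and other binary variables of interest (e.g., methylation". The next sentence covers all of these: "These correlation coefficients can be sorted in descending order to help identify the top candidates of physiologic and biochemical markers". Nothing separates or rescales the binary coefficients before the sort.

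The laboratory side is in Section 7.1. Methylation-specific PCR (MSP) on intake buccal cells gives a call for each of ten panel genes: "Methylated (M) or unmethylated (U) status will be denoted per gene per participant". Pyrosequencing is a firm commitment for LINE-1. For the panel genes it is worded as an option: "we can also use it for quantitative analysis of percent methylation of genes in the reference panel above". It is described there as a supplement to the MSP calls. Section 11.0 mentions methylation only as an example of a binary variable and names no analysis of percent methylation.

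**The concern.** A point-biserial coefficient is Pearson's r with one variable coded 0/1. When the call reflects an underlying continuous methylation level, cutting that level into two classes lowers the correlation with PM, and more so the further the methylated share lies from one half (for a symmetric exposure). Coefficients for hs-CRP, cytokines or blood pressure carry no such penalty. In one sorted list, a gene and a continuous marker that track PM equally well are not placed equally.

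The list is meant to point to the markers worth carrying into a larger study. Up to ten gene markers are on the compressed scale, and a measurement without that compression is described in the same protocol but not connected to the analysis.

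**Working it through.** **Inputs from the documents.** Section 11.0 enrols 14 drivers per arm and expects "n=11 per arm with analyzable (non-missing) data, assuming a 25% drop-out rate as described below". Check: 14 × (1 − 0.25) = 10.5, which rounds to the stated 11. Because the matrix is built within each group, each coefficient rests on 11 to 14 drivers.

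**Assumptions, not in the documents.** PM AUC is normally distributed. The share called methylated, p, is 50%, 20% or 10%. The call is a cut of a continuous methylation level that is jointly normal with PM.

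**Step 1: ceiling and attenuation.** If PM orders the drivers perfectly, the largest point-biserial coefficient is φ(z_p)/√(p(1−p)), where φ is the normal density and z_p the normal quantile. A latent correlation ρ becomes ρ times that ceiling.

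| p | φ(z_p) | √(p(1−p)) | Ceiling | Latent 0.50 becomes |
|---|---|---|---|---|
| 50% | 0.399 | 0.500 | 0.798 | 0.40 |
| 20% | 0.280 | 0.400 | 0.700 | 0.35 |
| 10% | 0.1755 | 0.300 | 0.585 | 0.29 |

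At these sample sizes with normal PM, the simulated mean ceiling at n=14 is 0.50 with one driver called methylated, 0.63 with two and 0.80 with seven. At n=11 it is 0.54, 0.67 and, with five, 0.80.

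**Step 2: other PM shapes.** With lognormal PM (log-SD 0.6 to 1.0) the mean ceiling at n=11 to 14 runs from about 0.27 to 0.81, depending on how many drivers are called methylated. Only a clearly two-cluster PM distribution split exactly by the call comes near 1 (about 0.96). Moving to Spearman does not remove the cap: its large-sample ceiling against a binary variable is √(3p(1−p)), which is 0.87, 0.69 and 0.52 at the three shares.

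**Step 3: effect on ranking (simulation, n=14).** These are the shares of runs in which the gene's coefficient exceeds the continuous marker's, among runs where the gene's coefficient is defined.

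| Latent correlation with PM | Percent methylation | Call, p=50% | Call, p=20% | Call, p=10% |
|---|---|---|---|---|
| Gene 0.6, marker 0.6 | about 50% | 33% | 26% | 22% |
| Gene 0.6, marker 0.3 | about 84% | 72% | 65% | 60% |
| Gene 0.6, marker 0 | about 96% | 91% | 88% | 86% |
| Gene 0, marker 0 | about 50% | 50% | 50% | about 50% |

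**Step 4: when there is no coefficient.** All n drivers share one call with probability pⁿ + (1−p)ⁿ. At p=10% this is 0.9¹⁴ = 0.23 for n=14 and 0.9¹¹ = 0.31 for n=11 (the pⁿ term is negligible). At p=20% it is 0.8¹⁴ = 0.04 and 0.8¹¹ = 0.09. Section 11.0 has no rule for this case.

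**The case against.** A reader might infer that the sort pushes gene markers down whatever their true association. The third and fourth rows of the ranking table show otherwise. The point-biserial coefficient has the same null spread as Pearson's r (SD about 0.28 at n=14 for both), so an unassociated gene ties with an unassociated marker, and an associated gene usually still outranks a weaker marker. The loss is attenuation, and it bites when true associations are similar.

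A reader might also infer that the analysis section takes a continuous measurement and dichotomises it, or that percent methylation is already in hand for every gene. The documents support neither. The M/U call is what MSP delivers, and nothing says that pyrosequencing values will be converted to calls or discarded. The general Pearson or Spearman rule could cover them as it stands. Pyrosequencing is certain only for LINE-1, and making it compulsory for ten panel genes would add laboratory work in a study whose size was set mainly by resources.

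Two further points stand. Sampling error is large: the Fisher 95% interval around r = 0.50 is about −0.14 to 0.85 at n=11 and −0.04 to 0.81 at n=14, so any ordering is loose. And the buccal swab is taken once, at intake, before the 28-day PM AUC accrues. Percent methylation does not cure that.

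What survives is narrow. As written, coefficients on different scales may share one ranking, and the analysis section is silent on a continuous methylation measure that the laboratory section describes.

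**Conclusion.** The point holds as a minor improvement. An M/U gene with the same latent correlation (0.6) as a continuous marker ranks first in about 33%, 26% or 22% of runs at n=14, for methylated shares of 50%, 20% and 10%, against about 50% with percent methylation. Those figures rest on normal PM and on assumed shares. The documents give neither, and the plan itself allows for skew, so the size of the effect is a range and not a fixed number. No error rate is affected, because the plan is descriptive only, the sort is worded as something that can be done, and no cut-off is attached to it. The intake-only buccal sample further limits what any methylation ranking can show.

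**What to change.** In Section 11.0, Aim 1b:

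- Correlate percent methylation (LINE-1, and any panel gene that is pyrosequenced) with PM AUC under the plan's existing Pearson-unless-skewed rule, and rank on that value in preference to the M/U call.
- Report M/U calls as counts per gene and group.
- Rank genes that have M/U calls only in a separate list, and mark the coefficient as not estimable when every driver in a group has the same call.
- State beside any methylation ranking that the sample was taken at intake.

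The cost is a change of wording before analysis, with no new assay required. The price is that there is no single combined ranking, and that percent methylation of panel genes enters only where the optional pyrosequencing is actually run.

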The Harvard Six Cities Study was the first large, prospective cohort study that demonstrated that chronic exposure to air pollutants is independently related to cardiovascular mortality (3). It showed that elevations of $PM_{2.5}$ and sulfates demonstrated the strongest associations with CVD. Fine particulate air pollution is a risk factor for CVD via mechanisms that likely include altered cardiovascular autonomic function (associations have been seen between elevations in $PM_{2.5}$ and increases in systolic blood pressure (30) and reduced heart rate variability (31-38), inflammation, and accelerated atherosclerosis (5, 39-41). Short-term exposure to PM has been associated with elevated proinflammatory markers, including interleukin 1-beta (IL-1 β), interleukin 6 (IL-6), tumor-necrosis-factor alpha (TNF- α), and high sensitivity C-reactive protein (hs-CRP), which may potentially mediate harmful subclinical cardiovascular effects (30, 42-45). There is epidemiologic evidence that CRP is a strong predictor of future CVD risk (46) and that elevated hs-CRP is highly associated with poor cardiovascular prognosis (47, 48). DRIIVE will contribute to the understanding of the associations between these mechanisms and increased CVD risk.

Products of diesel combustion, such as polycyclic aromatic hydrocarbons (PAHs), are also relevant to drivers (164, 165). Many individual PAHs are genotoxic carcinogens (165). One of the parent PAHs, pyrene, is metabolized to 1-hydroxypyrene and excreted in the urine, has been widely used as a biomarker for PAH exposure, and has been shown to be elevated in studies including taxi drivers (166-168). Increased incidences of cancer have been associated with occupational PAH exposure, including lung cancer (169). PAHs may also contribute to the atherosclerotic process and inflammation, increasing cardiovascular disease risk (170).

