Physiologic and biochemical markers will be measured by trained study staff twice per week and twice per day on 1 work day and 1 non-working day per week, for a total of four measurements per week (see section 7 for details). Physiologic and biochemical markers to be measured include: high-sensitivity C-reactive protein, blood pressure, and reduced heart rate variability – data to be downloaded via a smart phone (associated with CVD), and pro/anti-inflammatory cytokines (i.e., interleukin (IL)-1b, -6, -8, -10, tumor necrosis factor (TNF)-α, and interferon (IFN)-γ), and epigenetic changes associated with cancer and/or inflammation (see Figure 1 below and section 7 for details).

[figure not shown]

Figure 1: DRIVe Phase 1 - participant recruitment, screening, testing, intervention timeline in years 1, 2, and 3.

Polycyclic aromatic hydrocarbon (PAH) exposures will also be assessed through measurements of the urinary metabolite 1 hydroxy pyrene. Drivers will be asked to give a urinary sample in the morning after several days of work. They will be provided with a 100 cc sterilized polypropylene container. (Urinalysis Cup Kit). This will be collected by the study team, protected from sunlight and transported to *BAIC* for storage in a -20 degree freezer. Samples will ultimately be analyzed using liquid chromatography-tandem mass spectrometry (LC-MS-MS) by collaborating facility City College of New York. PAH exposures will also be measured through PUF sampler sized 10 cm by 2.2 cm diameter (171). Drivers will monitor PAH through PUF sampler one work day every week. The PUF filter will be placed in the vehicle of the drivers at the beginning of their work shift and picked up at the end of their shift. The study team will transport the sampler to the collaborating facility City College of New York for analysis.

The study team will be trained on screening and recruitment procedures, downloading DataRam results on PM measurements, on fingerstick blood, salivary, and buccal swab sampling procedures, and on storage/handling of samples (e.g. shipping dangerous goods training). Samples collected will be transported immediately by study staff to NYU for storage and analysis. If any critical abnormal/irregular health measurements are identified in the process of data collection, study staff will be trained to refer participant to low-cost health services.

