polypropylene container (Urinalysis Cup Kit). This will be collected by the study team, protected from sunlight and transported directly to *BAIC* for storage in a -20 degree freezer. Samples will ultimately be analyzed using liquid chromatography-tandem mass spectrometry (LC-MS-MS). This analysis will be carried out at the collaborating facility City College of New York.

- 10. PAH via PUF sampler** (measured at one work day each week): Drivers' PAH exposure will be measured through portable passive PUF sampler sized 10 cm by 2.2 cm diameter (171). Drivers will monitor PAH through PUF sampler one day every week. The PUF filter will be placed in the vehicle of the drivers at the beginning of their work shift and picked up at the end of their shift. Sampler will be transported to collaborating facility City College of New York for extraction and analysis. The PUF filter will be extracted using dichloromethane according to the method of Jaward et al. (172). The extracts will be concentrated using a Turbovap and cleaned before analysis. Parent PAHs will be analyzed with GC-MS in electron impact ion (EI) mode and selected ion monitoring (SIM), and nitro-PAHs and oxy-PAHs (quinones) will be analyzed via GC-NCI-MS and SIM (173).

Genes in the epigenetics reference panel for this study include ten (10) genes that have been informative as epigenetic biomarkers in air pollution or lung cancer studies (69). These are: **p16**- tumor suppressor, cell cycle regulator; **hMLH1**- mismatch DNA repair gene; **E-cadherin**- cell-cell adhesion molecule associated with epithelial to mesenchymal transition; **RARβ2**- binds retinoic acid, regulates cell growth/differentiation genes; **DAPK**- serine/threonine kinase involved in gamma-interferon induced apoptosis; **RASSF1A**- interacts with DNA repair protein XPA, inhibits cell cycle arrest; **RUNX3**, regulator of alveolar differentiation, frequently hypermethylated in lung adenocarcinomas; and **FHIT**, the most common gene inactivated in lung cancer besides p53. We also include a few inflammatory response genes: **IL-4**, whose promoter methylation decreased in mice exposed to diesel exhaust (DEP) and fungus (152) and **IFNg**, interferon gene whose methylation increased in DEP/fungus exposed mice.

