9.1 PRIMARY OUTCOMES

The primary outcomes are:

- To collect preliminary data on in-vehicle excess PM exposure the personal DataRam will monitor/report the PM levels as time-averaged sample (hourly averages) that will be monitored at work site and at homes across all groups
- To conduct a preliminary assessment of the correlation between PM exposure and physiologic and biochemical markers associated with increased risk of lung cancer and CVD the personal DataRam will monitor/report PM levels (hourly averages) that will be analyzed in comparison to increased systolic blood pressure, reduced heart rate variability, and presence of biological markers related to lung cancer and CVD risk.

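### Aim 1b ranks signed correlations from high to low, which read literally puts an inverse marker such as heart rate variability near the bottom; rank by absolute value instead

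*Combined protocol and SAP*

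**What the plan says.** Section 11.0, Aim 1b, builds a correlation matrix for each arm between PM area-under-the-curve summaries and the markers. Pearson is the default and Spearman is used if variables are skewed. For binary markers, "Point-biserial correlation coefficients will be sought between the continuous AUC summaries of PM data and other binary variables of interest". Then: "These correlation coefficients can be sorted in descending order to help identify the top candidates of physiologic and biochemical markers". The sentence gives its aim as finding the markers with the likeliest link to PM. It sets no cut-off, and it mentions neither absolute value nor a common direction of coding.

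Elsewhere the plan states the direction it expects:

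- **HRV.** Section 3.0 links PM to "increases in systolic blood pressure (30) and reduced heart rate variability (31-38". In Section 9.1 the second primary outcome has PM "analyzed in comparison to increased systolic blood pressure, reduced heart rate variability, and presence of biological markers". Section 4.3 lists "high-sensitivity C-reactive protein, blood pressure, and reduced heart rate variability".
- **LINE-1 methylation.** Section 7.1: "Recent studies show decreased LINE-1 methylation following exposure to traffic particulates".
- **IL-4 methylation.** Section 7.1 describes this gene as one "whose promoter methylation decreased in mice exposed to diesel exhaust (DEP) and fungus".

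For the ten-gene panel, Section 7.1 says: "Methylated (M) or unmethylated (U) status will be denoted per gene per participant". It gives no numeric code for the two calls. The same section adds that pyrosequencing can also supply percent methylation for these genes.

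**The concern.** All three coefficients run from -1 to +1. A high-to-low sort of signed values puts strong positive associations first, null markers in the middle and strong negative ones last. The sentence is meant to pick out strength of association, but the rule as written picks out positive association only.

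HRV is one of only two markers that the second primary outcome names individually, and it is recorded daily. If the plan's own expectation is right, its coefficient is negative, and the stronger the true relation the lower it ranks. Section 11.0 describes no other device for choosing markers, and the pilot is meant to guide a larger trial. A list produced literally by this rule could favour noise over a real HRV signal.

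The binary methylation calls raise a related problem. Their signed rank depends on which call is coded 1.

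**Working it through.** **The plan's own figure.** Section 11.0 recruits 14 per arm and allows 25% dropout: 14 × (1 - 0.25) = 10.5, rounded up to the stated 11 analyzable. The matrix is built by arm, so n = 11 is used below.

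**Number of markers, counted from the plan.** Systolic blood pressure, HRV and hs-CRP (3) + cytokines (6) + panel genes (10) + LINE-1 (1) + urinary 1-hydroxypyrene (1) = 21. With three PM components, 21 × 3 = 63 coefficients per arm. White-cell counts would add more. The illustration ranks 21, one coefficient per marker.

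**Methylation coding.** Swapping the 0/1 code changes each point-biserial coefficient from r to -r. A gene at +0.4 becomes -0.4 and moves from high to low in a signed sort. Since |r| does not change, ranking by |r| removes the dependence.

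**Assumptions not in the documents.** A top-5 cut, the true r values, normal data, and (except where stated) markers that are independent given PM. In each run, PM and 21 markers are drawn for 11 drivers with marker = r × PM + √(1 - r²) × noise. The 21 sample correlations are computed and ranked both ways. There were 10,000 to 40,000 runs per setting.

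One inverse marker and 20 nulls, chance that the inverse marker reaches the top 5:

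| True r | Signed sort | Sort by absolute value |
|---|---|---|
| -0.2 | 9.9% | 32.1% |
| -0.3 | 5.3% | 41.5% |
| -0.5 | 1.2% | 67.2% |
| -0.7 | 0.1% | 92.0% |

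Repeat runs agree within about one percentage point. Each null marker reaches the top 5 in about 24-25% of runs under the signed sort, so noise is listed more often than the inverse marker in every row. At r = -0.5 the median signed rank is 20th of 21. If the null markers are correlated at 0.6, the pairs become 19.9% against 36.6% (r = -0.2), 4.9% against 68.7% (r = -0.5) and 0.8% against 90.8% (r = -0.7).

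Three inverse markers, eight positive markers at r = +0.3 and ten nulls, chance for one given inverse marker:

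| True r | Signed sort | Sort by absolute value |
|---|---|---|
| -0.2 | 4.8% | 23.7% |
| -0.5 | 0.6% | 54.3% |

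Random ordering would give 5/21 = 23.8%. So for a weak inverse marker competing with many positive ones, sorting by |r| stops the penalty but does no better than chance.

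**Precision.** Around r = 0 at n = 11, the 95% CI half-width is tanh(1.96/√(11 - 3)) = 0.60. Any ranking at this size is loose, which is why the interval should be printed beside the rank.

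**The case against.** The strongest reply is that the authors meant strength. The purpose given in the sentence points that way, the wording is permissive, and the analysis is declared descriptive, with a full matrix in which a negative HRV coefficient would be plain to see. All of this stands. It makes the point a gap in wording. It does not make the rule as written match its purpose.

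The plan also calls the marker *reduced* HRV in several places, which could suggest that it is already scored in the adverse direction. No such scale is defined, and the phrase is not a coding rule.

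A reader might take LINE-1 and IL-4 as equally strong examples. They are not. Section 7.1 takes one buccal swab at Intake, before the 28-day PM summary accrues, so these values cannot have fallen in response to the measured exposure and at most track earlier exposure. The IL-4 evidence is also from mice with a fungal co-exposure. The coding problem affects only the binary calls, since percent methylation from pyrosequencing has a clear sign.

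A reader might also infer that Section 11.0 is wrong to name no within-driver statistic for daily HRV or repeated blood pressure. The documents do not support that. Section 11.0 already plans matching by time and defers the linking method. The own-control statement in Section 4.2 concerns before and after work and before and after the filter, not the Aim 1b correlations. A within-driver coefficient would answer a separate, short-term question.

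**Conclusion.** The point holds as a correction to the ranking rule, with HRV as the firm case. Read literally, the rule works against any inverse association, and the direction of that effect follows from sorting signed values, without the simulation. The size does rest on assumptions: the top-5 cut, the true correlations, one coefficient per marker, and the mix of null and positive markers. Under them the loss is modest for weak correlations and large for strong ones.

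It would be too strong to say that the plan will discard HRV or that the second primary outcome is compromised. No cut-off is set, the sort is optional, and the matrix would still show the coefficient. No stated error rate or sample size changes, because the plan states no alpha or power. The change is worth making because it is nearly free and protects a marker named in a primary outcome.

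**What to change.** In Section 11.0, Aim 1b, replace the high-to-low sort with wording such as: *coefficients will be ranked by absolute value, with the sign and 95% CI shown and the number of correlations examined stated*. Add the 0/1 code for methylated and unmethylated calls, or use percent methylation where pyrosequencing supplies it.

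This costs one sentence and a short coding note, and needs no new data.

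If the team wishes, a descriptive within-driver analysis of daily HRV against daily PM could be added as an optional supplement, labelled as a short-term association. It is not needed to resolve this point.
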